7.5.3.2. RPV Sample Analysis

Plasma RPV analysis will be performed under the control of Janssen R&D. Concentrations of RPV will be determined in plasma samples using the currently approved bioanalytical methodology. Raw data will be archived at the bioanalytical site.

Once the plasma has been analyzed for RPV any remaining plasma may be used by the sponsor for further exploratory work on pharmacokinetics, metabolites, plasma protein binding, protein analysis, and biochemistry. No human DNA analysis will be performed on these samples.

7.6. Genetics

Information regarding genetic research is included in [Appendix 5: Genetic Research](#).

7.7. Viral Genotyping and Phenotyping

Whole venous blood samples will be obtained from each participant to provide PBMCs and plasma for storage samples according to the Time and Events Table (see Section 7.1) for potential viral genotypic and phenotypic analyses.

Details concerning the handling, labeling and shipping of these samples will be supplied separately. Genotypic and phenotypic analyses may be carried out by Monogram Biosciences using, but not limited to, their Standard PhenoSense and GenoSure testing methods for protease (PRO), reverse transcriptase (RT), and integrase assays.

7.7.1. HIV-1 Polymerase Viral Genotyping and Phenotyping

Participants meeting confirmed virologic failure will have plasma samples tested for HIV-1 PRO and RT genotype and phenotype and HIV-1 integrase genotype and phenotype from samples collected at the time of meeting suspected virologic failure; these results will be reported to the investigator as soon as available to provide guidance for election of an alternative regimen.

7.7.2. HIV-1 Exploratory Analysis

Additional analyses for HIV-1 resistance may, for example, be carried out on peripheral blood mononuclear cell (PBMC) samples collected at Baseline and/or on stored blood samples from other relevant time points. These analyses may include but are not limited to additional viral genotyping and/or phenotyping, as well as other virologic evaluations such as linkage and minority species analyses, low level HIV-1 RNA quantitation and measurement of viral replicative capacity. HIV-1 PRO and RT genotype and phenotype and HIV-1 integrase genotype and phenotype will also be determined on the last on-treatment isolates from participants who have HIV-1 RNA ≥ 200 c/mL regardless of confirmatory HIV-1 RNA.

7.8. Value Evidence and Outcomes

Health outcomes assessments will be conducted according to the Time and Events Table (Section 7.1). Assessments are recommended to be administered with a paper instrument at the beginning of the visit prior to collection of blood for analysis and other scheduled assessments.

The “Preference” questionnaire will assess whether patients prefer the CAB LA + RPV LA injectable treatment or the daily oral ARV regimen, and assess preference for the CAB LA + RPV LA Q8W regimen or CAB LA + RPV LA Q4W regimen. The “Preference” questionnaire will include 3 questions evaluating preference of HIV treatment and the attributes supporting this preference.

The HIV Treatment Satisfaction Questionnaire (HIVTSQ) [Woodcock, 2001 and Woodcock, 2006] was developed to evaluate treatments for HIV and patient satisfaction. The original HIVTSQ included 10 items and underwent two stages of psychometric validation (Woodcock, 2001, Woodcock, 2006). Recently, the HIVTSQ was adapted to include injectable treatment for HIV following a qualitative study with HIV patients in five European countries. The adaptation of the HIVTSQ included two additional items related to the mode of administration (i.e., long acting intramuscular injection). These are:

CCI - This section contained Clinical Outcome Assessment data collection questionnaires or indices, which are protected by third party copyright laws and therefore have been excluded.

Psychometric analyses from three datasets (one from the UK, one from the USA and one from the LATTE-2 trial) reveal that the addition of two items in the original version of the HIVTSQ is suitable and does not reduce the overall validity of the questionnaire. The current study will be using the HIVTSQs (status version) and the revised HIVTSQc (change version) of this recently developed HIVTSQ 12-item questionnaire. The HIVTSQ 12-item questionnaire retains the option of calculating the total score as if it only had the original 10 items (as the original 10 items are included in the HIV-TSQ12). In addition, it allows for calculation of an 11-item scale score including the “CCI [REDACTED]” item (item-11). The “CCI [REDACTED]” item (item-12) will be included in the questionnaire as a stand-alone item to evaluate potentially painful injectables. These measures will assess change in treatment satisfaction over time (in the same participants) and compare current satisfaction with previous treatment satisfaction, from an earlier time point.

The Perception of Injection (PIN) questionnaire explores the bother of pain at the injection site and ISR, anxiety before and after injection, willingness to receive an HIV injectable treatment the following visit and satisfaction with the mode of treatment administration of individuals receiving injection and perceptions of individuals associated with receiving injections. The PIN questionnaire was derived from the Vaccines' Perception of Injection (VAPI) questionnaire (Chevat, 2009), and adapted for HIV-infected patients who will receive the CAB LA and RPV LA regimen. This measure contains 21 items that measure pain at injection site, local site reactions, impact on functioning and willingness to pursue injectable treatment outside of a clinical trial. Scores range from 1 to 5, and questions are phrased in such a way as to ensure that 1 always equated with the most favourable perception of vaccination, and 5 the most unfavourable.

The ACCEPT questionnaire is a generic medication acceptance measure assessing how patients weigh advantages and disadvantages of long-term medications (Marant, 2012). ACCEPT may be a predictor of patients' future adherence to and/or persistence with their treatment. While the ACCEPT questionnaire consists of 25 items that capture six dimensions, we will use three questions that focus on general acceptance of study medication.

The HIV/AIDS Targeted Quality of Life (HAT-QoL) instrument [Holmes, 1998] originally contained 42 items, grouped into nine dimensions, assessing overall function and well-being. For the purposes of this study, ViiV Healthcare is using a shorter version adapted from the original version. This shorter version contains 14 items grouped into the three following dimensions: “life satisfaction”, “disclosure worries” and “HIV medication”. All items use a “past 4 weeks” timeframe and a Likert response scale from 1=“all of the time” to 5=“none of the time”

The “Reason for Switch” question will contain a single item exploring the reasons why patients choose to switch study medication. The single item will include six possible response options.

Qualitative interviews may be conducted regarding their experience with study treatment. These would be conducted under a separate IRB approved consent. Participation in the interviews would be voluntary.

7.8.1. Value Evidence and Outcomes Endpoints (Secondary)

- The “Preference” questionnaire will assess preference for CAB LA + RPV LA every 8 weeks or CAB LA + RPV LA every 4 weeks compared to oral ARV regimen, and preference for CAB LA + RPV LA every 4 weeks compared to CAB LA + RPV LA every 8 weeks at Week 48 (or Withdrawal).
- Change from Week 8 in Dimension scores (e.g., “Bother of ISRs”, “Leg movement”, “Sleep”, and “Injection Acceptance”) and individual item scores assessing pain during injection, anxiety before and after injection, willingness to be injected in the future and overall satisfaction with mode of administration over time using the Perception of iNjection questionnaire (PIN) at Weeks 24, and 48 (or Withdrawal).
- Proportion of participants considering pain and local reactions following injection to be extremely or very acceptable based on the acceptability score over time using the Perception of iNjection questionnaire (PIN).
- Change from Baseline (Day 1) in total “treatment satisfaction” score, and individual item scores of the HIVTSQs at Weeks 24, 48 (or Withdrawal).
- Change in treatment satisfaction over time (using the HIVTSQc) at Week 48 (or Withdrawal).
- Change from Baseline (Day1) in treatment acceptance (at Weeks 24 and 48 (or Withdrawal from the study) using the “General acceptance” dimension of the Chronic Treatment Acceptance (ACCEPT) questionnaire.
- Change from Baseline (Day1) in HR QoL (using the HAT-QoL short form) at Weeks 24, and 48, (or Withdrawal).

7.8.2. Value Evidence and Outcomes Endpoints (Exploratory)

- The “Reason for Switch” question will be administered at Day 1 (Baseline) for patients randomized from oral SOC, to assess the reasons for willingness to switch ART.
- The “Reason for Switch” question will be administered at Day 1 (Baseline) for patients randomized from CAB LA + RPV LA every 4 weeks in ATLAS, to assess the reasons for willingness to continue long-acting ART.

7.8.3. Guidance for administering the different versions of HIVTSQc, Preference and Reason for Switch Questionnaires in ATLAS-2M

For the questionnaires not included below, HIVTSQs, HAT-QoL, ACCEPT and PIN, there only exists one version of each PRO that will be administered to all patients.

Questionnaire	Version	Week visit in ATLAS-2M	Treatment Arm in ATLAS-2M	Treatment before entering ATLAS-2M	Patients in Extension phase in ATLAS
HIVTSQc	Q4W ATLAS to Q4W ATLAS-2M	Week 48 / Withdrawal	Currently on Q4W	Randomized at Day 1 in Q4W arm in ATLAS	Even if patients remained in extension phase in ATLAS consider only the initial arm they were randomized in Day 1 in ATLAS
	Q4W ATLAS to Q8W ATLAS-2M	Week 48 / Withdrawal	Currently on Q8W	Randomized at Day 1 in Q4W arm in ATLAS	
	SOC to Q4W or Q8W ATLAS-2M	Week 48 / Withdrawal	Currently on Q4W or Q8W	Any SOC treatment: Randomized at Day 1 in SOC in ATLAS or coming outside of ATLAS	
Preference	Injection to Injection treatment	Week 48 / Withdrawal	Currently on Q8W	Randomized at Day1 in Q4W arm in ATLAS	Even if patients remained in extension phase in ATLAS consider only the initial arm they were randomized in Day 1 in ATLAS
	Oral to Injection treatment	Week 48 / Withdrawal	Currently on Q4W or Q8W	Any SOC treatment: Randomized at Day 1 in SOC in ATLAS or coming outside of ATLAS Continuing Q4W from ATLAS	

Questionnaire	Version	Week visit in ATLAS-2M	Treatment Arm in ATLAS-2M	Treatment before entering ATLAS-2M	Patients in Extension phase in ATLAS
Reason for Switch		Day 1	Currently on Q4W or Q8W	Any SOC treatment: Randomized at Day 1 in SOC in ATLAS or coming outside of ATLAS	Administer again even if patients were administered the “reason for switch” at week 52 in ATLAS.
Reason for Continuation		Day 1	Currently on Q4W or Q8W	Randomized at Day 1 in Q4W arm in ATLAS	

8. DATA MANAGEMENT

- For this study participant data will be entered into GSK defined eCRFs, transmitted electronically to GSK or designee and combined with data provided from other sources in a validated data system.
- Management of clinical data will be performed in accordance with applicable GSK standards and data cleaning procedures to ensure the integrity of the data, e.g., removing errors and inconsistencies in the data.
- Adverse events and concomitant medications terms will be coded using Medical Dictionary for Regulatory Activities (MedDRA) and an internal validated medication dictionary, GSKDrug.
- eCRFs (including queries and audit trails) will be retained by GSK, and copies will be sent to the investigator to maintain as the investigator copy. Participant initials will not be collected or transmitted to GSK according to GSK policy.

9. STATISTICAL CONSIDERATIONS AND DATA ANALYSES

The study is designed to demonstrate that the antiviral effect of Q8W dosing with CAB LA + RPV LA is non-inferior to Q4W dosing CAB LA + RPV LA in subjects stably suppressed on an oral SOC regimen or Q4W CAB LA + RPV LA regimen prior to randomization. Non-inferiority in the proportion of participants with HIV-RNA ≥ 50 c/mL at Week 48 (defined by the US FDA snapshot algorithm) can be concluded if the upper bound of a two-sided 95% confidence interval for the difference between the two treatment arms (Q8W – Q4W) is less than 4%.

If f_{Q8W} is the snapshot failure rate for Q8W CAB LA + RPV LA, and f_{Q4W} is the snapshot failure rate for Q4W CAB LA + RPV LA then the hypotheses can be written as follows:

$$H_0: f_{Q8W} - f_{Q4W} \geq 4\% \quad \text{vs} \quad H_1: f_{Q8W} - f_{Q4W} < 4\%$$

9.1. Sample Size Considerations

. This study will randomize approximately 510 participants per arm. Assuming the true proportion with HIV-1 RNA ≥ 50 c/mL is 3% for the Q8W arm and 2% for the Q4W arm, a non-inferiority margin of 4%, and a 2.5% one-sided significance level, this sample size would provide at least 85% power to show non-inferiority at Week 48 (using unpooled Z test statistic). With this sample size, 90% power would be achieved assuming a 1% treatment difference and true proportions with HIV-1 RNA ≥ 50 c/mL of 2.63% for the Q8W arm and 1.63% for the Q4W arm.

With 510 subjects per arm and assuming an observed proportion HIV-RNA ≥ 50 c/mL is 2% for Q4W, the largest observed treatment difference to achieve non-inferiority with respect to a 4% margin is 1.92 percentage points. This equates approximately to observing an excess of 10 subjects on the Q8W arm (10 subjects on Q4W vs. 20 subjects on Q8W).

This sample size of 510 participants per arm will also provide at least 90% power (using unpooled Z test statistic) to show non-inferiority in the proportion of participants with plasma HIV-1 RNA < 50 c/mL (per FDA's snapshot algorithm) at Week 48 over a range of true response rates, on the basis of a -10% non-inferiority margin and 2.5% one-sided significance level (see [Figure 15](#)). For example, assuming true response rate for the Q8W arm and Q4W arm are both 92%, the power is $\geq 99\%$ to show non-inferiority for this key secondary endpoint.

9.1.1. Rationale for non-inferiority margin

A non-inferiority margin of 4% has been chosen for this study because a snapshot proportion with HIV-1 RNA ≥ 50 c/mL at Week 48 in this range is considered clinically tolerable given the Q8W regimen will offer important advantages over the Q4W regimen such as reduced injection frequency, and may offer better adherence and treatment satisfaction. This margin is also in concordance with the current FDA Guidance for Industry (FDA, 2015), which is the most current regulatory guidance from either the European Medicines Agency (EMA) or FDA and includes specific recommendations regarding switch studies.

9.1.2. Assumption for Snapshot Proportion with HIV-RNA ≥ 50 c/mL at Week 48 (Primary Endpoint)

For the sample size calculation, assumptions regarding the true proportion with HIV RNA ≥ 50 c/mL for each arm were informed by data from the LATTE-2 Phase 2b study ([Table 11](#)). These data suggest a rate of 2% for Q4W and a possibly higher rate in the neighbourhood of 3% for Q8W.

Two important changes to the current study in relation to the LATTE-2 study were also considered in setting the sample size. Firstly, the loading dose schedule for Q8W has been modified in an attempt to optimize the pharmacokinetics of CAB LA + RPV LA. Secondly, a re-testing strategy (see Section 5.5.5.1) has been added to reduce the number of subjects counted as having HIV RNA ≥ 50 c/mL in the primary analysis at key timepoints because of transient blips (consistent with the FDA's guidance for the Snapshot endpoint). Through these changes, it is possible that the proportions with HIV RNA ≥ 50 copies/mL will be lower than that observed in the LATTE-2 study.

Table 11 Snapshot Analysis Outcomes for LATTE-2 Phase IIb Study of CAB LA + RPV LA (Intent-to-Treat Maintenance Exposed Population)

Week 48			
Study	Maintenance Treatment Arm	HIV-RNA <50	HIV-RNA ≥ 50
LATTE-2 (ITT-ME) ^a	CAB LA + RPV LA Q8W (N=115)	92%	8/115 (7%)
	CAB LA + RPV LA Q4W (N=115)	91%	1/115 (<1%)
	Pooled LA (N=230)	92%	6/230 (4%)
	Oral CAB + 2NRTIs (N=56)	89%	1/56 (2%)
Week 96			
LATTE-2 (ITT-ME) ^b	CAB LA + RPV LA Q8W (N=115)	94%	5/115 (4%)
	CAB LA + RPV LA Q4W (N=115)	87%	0/115 (0%)
	Pooled LA (N=230)	90%	5/230 (2%)
	Oral CAB + 2NRTIs (N=56)	84%	5/56 (2%)

- a) Participants had HIV-1 RNA <50 c/mL at Week -4 and received oral CAB 30 mg + 2 NRTIs as initial induction period therapy from Week -20 to Day 1.
- b) Participants had HIV-1 RNA <50 c/mL at Week 20 and switched from oral CAB 30 mg + 2 NRTIs to Oral CAB 30 mg + RPV at Week 24.

9.1.3. Assumption for Response Rate at Week 48 (Secondary Endpoint)

Given the response rates shown in Table 11, a reasonable assumption for the true response rate (HIV-1 RNA <50 c/mL) for both arms is 92%.

9.1.4. Sample Size Sensitivity

Figure 15a (left panel) shows the sensitivity of the power curve for the primary comparison to different assumed 'true' proportions with HIV-RNA ≥ 50 c/mL with 510 randomized participants per arm based on calculations using an unpooled Z test statistic and asymptotic approximation. For example, if the true rate for Q8W is 1.5 percentage points higher than Q4W (green line), then the study would still have over 80% power to meet its primary objective if the Q4W rate is less than 1.3%.

Figure 15b (right panel) shows the impact on power to changes in the sample size assuming a 2% true-rate for Q4W. Power remains at least 80% for sample sizes as low as 425 per arm if the true Q8W rate is at most 1-percentage point inferior to Q4W.

Figure 15 Sensitivity of Estimated Power for Snapshot Proportion with HIV-RNA \geq 50 c/mL

[figure not shown]
[figure not shown]

Figure 16a (left panel) shows the sensitivity of the estimated power for the secondary endpoint comparison of response rates (HIV-1 RNA <50 c/mL at Week 48) to different assumed ‘true’ response rates based on calculations using an unpooled Z test statistic and asymptotic approximation. For example, if the true Q8W rate is two percentage points inferior to Q4W (blue line), then power is at least 90% for Q4W rates greater than 82%.

Figure 16b (right panel) shows the impact on power to changes in the sample size assuming an 92% response rate for Q4W. For example, if the true Q8W rate is 3- percentage points inferior to Q4W (green line), then power remains at least 90% for sample sizes as low as 368 per arm.

Figure 16 Sensitivity of Estimated Power for Snapshot Proportion with HIV-RNA <50 c/mL

9.1.5. Sample Size Re-estimation or Adjustment

No sample-size re-estimation based on response data is planned for this study.

9.2. Data Analysis Considerations

9.2.1. Analysis Populations

9.2.1.1. Intent-to-Treat Exposed (ITT-E)

The ITT-E population will consist of all randomly assigned participants who receive at least one dose of study drug. Participants will be assessed according to their randomized treatment, regardless of the treatment they received. The population used in the primary efficacy analysis will be the ITT-E population.

9.2.1.2. Per-Protocol Population (PP)

The Per-Protocol (PP) Population will consist of all participants in the ITT-E Population with the exception of major protocol violators. The PP will be used for sensitivity analysis of the primary endpoint.

9.2.1.3. PK Population

The PK Population will include all participants who receive CAB and / or RPV and undergo PK sampling during the study, and provide evaluable CAB and /or RPV plasma concentration data. Participants in this population will be included in the PK analysis.

9.2.1.4. Safety Population

The Safety Population will consist of all randomly assigned participants who receive at least one dose of study drug. Participants will be assessed according to actual treatment received. Unless otherwise stated, the Safety Population will be used for safety analyses.

9.2.2. Treatment Comparisons

9.2.2.1. Primary Comparison of Interest

The primary analysis will be based on the ITT-E population. The primary comparison will be made at a one-sided 2.5% level of significance. Treatment with Q8W will be declared non-inferior to Q4W if the upper end of a two-sided 95% confidence interval for the difference between the two groups (Q8W – Q4W) in the proportion of participants with HIV-RNA ≥ 50 c/mL at Week 48 (defined by the US FDA snapshot algorithm) lies below 4%.

9.2.2.2. Other Comparisons of Interest

- The analysis described above will also be performed using the PP population and the results will be compared for consistency with the results from the ITT-E population. If the primary comparison on interest using the ITT-E population demonstrates non-inferiority of Q8W compared to Q4W then the following key secondary comparisons will be tested: Treatment with Q8W will be declared non-inferior to Q4W with respect to the proportion of participants with HIV-1 RNA < 50 copies/mL at Week 48 (defined by the US FDA snapshot algorithm) if the lower end of a two-sided 95% confidence interval for the difference between in rates (Q8W – Q4W) lies above -10% using the ITT-E population
- Superiority of Q8W compared to Q4W with respect to change from baseline HIVTSQs total score at Week 48 using the ITT-E population and a two-sided 5% level of significance

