using the variance estimator given by [Sato, 1989], which is consistent in both sparse data and large strata. The formula for computing the Sato variance estimate will be provided in the RAP. Non-inferiority will be declared if the upper bound of the two-sided 95% confidence interval for the difference (Q8W – Q4W) is less than 4%.

The weighted least squares chi-squared statistic [Fleiss, 1981] will be used to assess evidence of treatment difference heterogeneity across strata. strata, Following Lui and

Kelly [Lui, 2000], 0.50 will be added to each cell in any strata for which the stratum-specific rate estimates of either f_{Q8W} or f_{Q4W} are zero or one. Any heterogeneity found to be statistically significant will be explored. Stratum-specific analyses will also be provided. Investigation of heterogeneity will be confined to the primary endpoint. Tests of homogeneity will be assessed at the one-sided 10% level of significance. Full details will be contained in the RAP.

On-treatment data collected from extra visits within a window will be included in the derivation of the Snapshot response/failure but summary tables using observed case (OC) datasets will only use the data captured closest to the target visit date. Detailed explanations of the derivation of visit windows will be included in the RAP. Any changes to the original analysis plan in the protocol will be described in the RAP and/or clinical study report (CSR).

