9.3.7. Health Outcomes Analyses

Details of the analyses to be performed for the endpoints described in Section 7.8 will be specified in the reporting and analysis plan. Participant preference for CAB LA + RPV LA every 8 weeks or CAB LA + RPV LA every 4 weeks compared to oral ARV regimen, and preference for CAB LA + RPV LA every 4 weeks compared to CAB LA + RPV LA every 8 weeks will be a key secondary treatment analysis based on the ITT-E population. As another key secondary treatment comparison, superiority of Q8W compared to Q4W

with respect to change from baseline in HIVTSQs total score at Week 48 will be tested at a two-sided 5% significance level using a linear model based on the ITT-E population.

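### After the primary passes, 9.2.2.2 tests two key secondary comparisons at full level with no stated order, and 9.3.7 adds preference as key secondary with no test and an ill-fitting population

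*Protocol*

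**What the plan says.** - **Primary (9.2.2.1, 9.3.1).** "The primary comparison will be made at a one-sided 2.5% level of significance". The rule is that "Non-inferiority will be declared if the upper bound of the two-sided 95% confidence interval for the difference (Q8W – Q4W) is less than 4"%.
- **Gate and list (9.2.2.2).** If the primary succeeds in ITT-E, "then the following key secondary comparisons will be tested". Two comparisons follow. One is non-inferiority in the proportion with HIV-1 RNA <50 c/mL at Week 48, judged by a two-sided 95% CI against -10 points. The other is "Superiority of Q8W compared to Q4W with respect to change from baseline HIVTSQs total score at Week 48", in ITT-E at a two-sided 5% level. No order, alpha split or dependence between them is given.
- **Health outcomes (9.3.7).** The HIVTSQs test is repeated as another key secondary comparison at two-sided 5%. Preference (each injectable regimen against oral therapy, and Q4W against Q8W) "will be a key secondary treatment analysis based on the ITT-E population". Preference is not in the 9.2.2.2 list, and no hypothesis, test or level is attached to it.
- **Who gets which preference form (7.8.3).** The Injection-to-Injection form goes to participants on Q8W who were randomised to Q4W at ATLAS Day 1. All entrants from oral standard of care, in both arms, and those continuing Q4W get the Oral-to-Injection form. For people who stayed into the ATLAS Extension Phase, sites are told to "consider only the initial arm they were randomized in Day 1 in ATLAS".
- **Multiplicity statements (9.2.3.1, 9.2.3.2).** These explain why the Week 24 and IDMC looks need no adjustment of the primary. Nothing comparable covers the key secondary tests.

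**The concern.** There are two separate problems.

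The first is error control among the key secondary claims. The gate protects the primary. Once it opens, two tests each carry one-sided 2.5% in favour of Q8W, and nothing in the text makes either depend on the other. HIVTSQs is a self-reported satisfaction score in an open-label trial. A claim on it could be presented as confirmatory even if the <50 c/mL comparison had failed.

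The second is the content of the key secondary set. 9.2.2.2 and 9.3.7 disagree on whether preference belongs to it. The population named for preference, ITT-E, does not match the people who receive the form that compares one injection schedule with the other. A reader cannot tell from the Protocol which of these results count as confirmatory, or what the denominator of a Q8W-against-Q4W preference percentage would be.

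**Working it through.** **Inputs.** From 9.1: "This study will randomize approximately 510 participants per arm", and "Assuming the true proportion with HIV-1 RNA ≥ 50 c/mL is 3% for the Q8W arm and 2% for the Q4W arm", with a 4-point margin, one-sided 2.5%, an unpooled Z test and stated power of at least 85%. Also from 9.1: 92% response in both arms for the key secondary, with a 10-point margin and stated power of at least 99%. The levels of the two key secondary tests come from 9.2.2.2.

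**1. Reproduce the Protocol's own figures.**
- Primary: SE = √[(0.02×0.98 + 0.03×0.97)/510] = 0.00977. Power = Φ[(0.04 - 0.01)/0.00977 - 1.96] = 86.7%. Stated: at least 85%. It reproduces.
- <50 c/mL: SE = √[2×0.92×0.08/510] = 0.0170. Power = Φ[0.10/0.0170 - 1.96], above 99.9%. Stated: at least 99%. It reproduces.

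**2. Error among the two listed tests once the gate is open.** A false claim favouring Q8W has probability 0.025 on each test when its null is true (two-sided 5% for HIVTSQs is 2.5% in that direction).
- Both nulls true, tests independent: 1 - 0.975² = 4.94%. The upper bound under any dependence is 0.025 + 0.025 = 5.0%.
- Positively correlated tests (bivariate normal simulation): 4.5% at correlation 0.5 and 3.9% at 0.8.
- Allowing for an 86.7% chance of passing the gate, taken as independent: 0.867 × 4.94% = 4.3%.
- Primary null true: the gate holds any false key secondary claim to 2.5% or less.
- Only the HIVTSQs null true: 2.5%, because a claim on <50 c/mL would then be correct.

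**3. Error under a fixed sequence (primary, <50 c/mL, HIVTSQs).** If the <50 c/mL null is true, no false claim can occur unless that test is wrongly passed, at 2.5%. If it is false, only HIVTSQs can go wrong, at 2.5% in favour of Q8W. The maximum is 2.5% in either case. HIVTSQs is blocked only when <50 c/mL fails, which has probability below 0.1% at 92% in both arms.

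**4. Who receives the Injection-to-Injection form.** Let s be the share of the trial randomised to Q4W at ATLAS Day 1. The Protocol does not give s. With 1:1 randomisation about s/2 receive the form, all of them in the Q8W arm.

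| s (assumed) | Share given the form |
|---|---|
| 25% | 12.5% |
| 50% | 25% |
| 75% | 37.5% |
| 100% | 50% (510 of 1020) |

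Section 1.1 also admits participants on oral standard of care, so s is below 100% and the form reaches fewer than half of ITT-E.

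**5. A detail that affects the remedy.** Section 1.3 admits people randomised to standard of care in ATLAS who moved to Q4W in its Extension Phase. Under 7.8.3 they are classified by their initial arm and get the Oral-to-Injection form. Having received Q4W in ATLAS is therefore not the same as having been given the Injection-to-Injection form.

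**The case against.** The case against is substantial.

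**Order is read from silence.** 9.2.2.2 lists <50 c/mL first and HIVTSQs second and does not say they are tested simultaneously. Sections 9.2.3 and 9.3.7 leave detail to the reporting and analysis plan, which is not at hand and may set an order. This stands as a limit. It does not dispose of the point, because the Protocol itself fixes the gate, the tests and their levels, and 9.2.2.2 and 9.3.7 would still disagree about preference.

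**The 4.9% needs an unlikely state.** The <50 c/mL null means Q8W response at least 10 points lower. If the true excess of HIV-1 RNA ≥50 c/mL is under 4 points, the excess without evaluable data would have to exceed 6 points. The design assumes equal response. This stands: 4.9% is a worst case, and the sequence would rarely change a conclusion.

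**Preference may be meant descriptively.** 9.3.7 calls preference an analysis and HIVTSQs a comparison. Using ITT-E does not prove that people who were not asked enter the denominator. The questionnaire items are not shown, so placing the Q8W-against-Q4W question in the Injection-to-Injection form rests on its name and allocation. A descriptive reading is possible; the Protocol should say so.

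**Stronger readings that the documents do not support.**
- A reader might infer 7.4% (1 - 0.975×0.95). That counts HIVTSQs differences favouring Q4W, whereas the claim is superiority of Q8W.
- A reader might add two preference tests at 5% and reach 16.4% (1 - 0.975×0.95³). The Protocol specifies no such tests.
- A reader might take form allocation as a cause of lost error control. It affects the population and the quantity estimated, not type I error.

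**Conclusion.** The point holds in a limited form. After primary success, the two listed key secondary tests run at full level with no stated order. A false key secondary claim favouring Q8W can therefore reach about 4.9% instead of one-sided 2.5%. That figure assumes both nulls are true and the tests are independent; it is smaller under positive correlation. The primary is unaffected, and if the primary null is true the gate already holds key secondary error to 2.5%.

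Preference is a separate inconsistency. It is called key secondary in 9.3.7, is absent from 9.2.2.2, has no test or level, and is tied to ITT-E although the Injection-to-Injection form reaches fewer than half of that population and nobody in the Q4W arm. No inflation can be attributed to it. The exact share cannot be computed, because the mix of entrants is not stated.

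This is worth correcting because the wording is easy to settle and the sequence costs almost no power. It does not threaten the main conclusion of the trial.

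**What to change.** 1. In 9.2.2.2 and 9.3.7, state one fixed sequence: the primary; then <50 c/mL non-inferiority at one-sided 2.5%; then, only if that is met, HIVTSQs superiority at two-sided 5%.
2. Remove the key secondary label from preference in 9.3.7 and report it descriptively among participants given each form. Report Q8W-against-Q4W preference among those given the Injection-to-Injection form. Define that group by the form received and not by any exposure to Q4W in ATLAS, so that Extension Phase switchers given the oral form are not counted in it.

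The cost is a wording change. The downside is that HIVTSQs superiority could not be claimed if the <50 c/mL comparison failed. That is very unlikely, since its power is over 99% under the planned response rates.
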